7.2.4 Dose Adjustment

There are no recommendations for or planned Rituximab dose adjustments. Doses can be held or skipped for toxicity, as summarized above.

7.3 Venetoclax

7.3.1 Formulation, Storage

It is a light yellow to dark yellow solid with the empirical formula C45H50CIN7O7S and a molecular weight of 868.44. Venetoclax has very low aqueous solubility.

Venetoclax must be stored at 15 to 25 degrees C (59-77 degrees F). Venetoclax is supplied from Research Supply, provided by Abbvie.

7.3.2 Dosage and Administration

Administration Guidelines from package insert:

Advise patients to take VENCLEXTA exactly as prescribed and not to change their dose or to stop taking VENCLEXTA unless they are told to do so by their doctor. Advise patients to take VENCLEXTA orally once daily, at approximately the same time each day, according to their doctor's instructions and that the tablets should be swallowed whole with a meal and water without being chewed, crushed, or broken.

Advise patients to keep VENCLEXTA in the original packaging during the first 4 weeks of treatment, and not to transfer the tablets to a different container.

Advise patients that if a dose of VENCLEXTA is missed by less than 8 hours, to take the missed dose right away and take the next dose as usual. If a dose of VENCLEXTA is missed by more than 8 hours, advise patients to wait and take the next dose at the usual time.

Advise patients not to take any additional dose that day if they vomit after taking VENCLEXTA, and to take the next dose at the usual time the following day.

7.3.3 Adverse Reactions and Precautions

The safety of single agent VENCLEXTA at the 400 mg recommended daily dose following a dose ramp-up schedule is based on pooled data of 240 patients with previously treated CLL from two phase 2 trials and one phase 1 trial. In the pooled dataset, the median age was 66 years (range: 29 to 85 years), 95% were white, and 69% were male. The median number of prior therapies was 3 (range: 1 to 12). The median duration of treatment with VENCLEXTA at the time of data analysis was approximately 10.3 months (range: 0 to 34.1 months). Approximately 46% of patients received VENCLEXTA for more than 48 weeks.

The most common adverse reactions (≥20%) of any grade were neutropenia, diarrhea, nausea, anemia, upper respiratory tract infection, thrombocytopenia, and fatigue.

Serious adverse reactions were reported in 43.8% of patients. The most frequent serious adverse reactions (≥2%) were pneumonia, febrile neutropenia, pyrexia, autoimmune hemolytic anemia (AIHA), anemia, and TLS.

In combination with rituximab, serious adverse reactions were reported in 46% of patients, with the most frequent (\geq 5%) being pneumonia (9%). The most common adverse reactions (\geq 20%) of any grade were neutropenia (65%), diarrhea (40%), upper respiratory tract infection (39%), fatigue (22%), cough (22%), and nausea (21%).

Discontinuations due to adverse reactions occurred in 8.3% of patients. The most frequent adverse reactions leading to drug discontinuation were thrombocytopenia and AIHA.

Dosage adjustments due to adverse reactions occurred in 9.6% of patients. The most frequent adverse reactions leading to dose adjustments were neutropenia, febrile neutropenia, and thrombocytopenia.

Specific warnings and precautions:

Tumor Lysis Syndrome

Tumor lysis syndrome, including fatal events and renal failure requiring dialysis, has occurred in previously treated CLL patients with high tumor burden when treated with VENCLEXTA.

VENCLEXTA can cause rapid reduction in tumor and thus poses a risk for TLS in the initial 5-week ramp-up phase. Changes in blood chemistries consistent with TLS that require prompt management can occur as early as 6 to 8 hours following the first dose of VENCLEXTA and at each dose increase.

Do not administer live attenuated vaccines prior to, during, or after treatment with VENCLEXTA until B-cell recovery occurs. The safety and efficacy of immunization with live attenuated vaccines during or following VENCLEXTA therapy have not been studied. Advise patients that vaccinations may be less effective.

Embryo-Fetal Toxicity

Based on its mechanism of action and findings in animals, VENCLEXTA may cause embryo- fetal harm when administered to a pregnant woman. In an embryo-fetal study conducted in mice, administration of venetoclax to pregnant animals at exposures equivalent to that observed in patients at the recommended dose of 400 mg daily resulted in post-implantation loss and decreased fetal weight. There are no adequate and well-controlled studies in pregnant woman using VENCLEXTA. Advise females of reproductive potential to avoid pregnancy during treatment. If VENCLEXTA is used during pregnancy or if the patient becomes pregnant while taking VENCLEXTA, the patient should be apprised of the potential hazard to the fetus.

7.3.4 Dose Adjustment and Management of Toxicity

There is no specific antidote for venetoclax. For subjects who experience overdose, closely monitor and provide appropriate supportive treatment; during ramp-up phase interrupt venetoclax and monitor carefully for signs and symptoms of TLS along with other toxicities. Based on venetoclax large volume of distribution and extensive protein binding, dialysis is unlikely to result in significant removal of venetoclax.

Dosing interruption and/or dose reduction may be required. See Table 3 for dose modifications for hematologic and other toxicities related to venetoclax. For subjects who have had a dosing interruption greater than 1 week during the first 5 weeks of ramp-up phase or greater than 2 weeks when at the daily dose of 400 mg, reassess for risk of TLS to determine if reinitiation with a reduced dose is necessary (eg, all or some levels of the dose ramp-up schedule).

Table 4. Venetoclax Recommended Dose Modification for Toxicities:

Event	Occurrence	Action	
Tumor Lysis Syndrome			
Blood chemistry changes or symptoms suggestive of	Any	Withhold the next day's dose. If resolved within 24-48 hours of last dose, resume at the same dose.	
TLS (see Howard Criteria in Appendix E)		For any blood chemistry changes requiring more than 48 hours to resolve, resume at a reduced dose (see Table 5)	
		For any events of clinical TLS ^b , resume at a reduced dose following resolution (see Table 5).	
	Non-H	ematologic Toxicities	
Grade 3 or 4 non- hematologic toxicities	l st occurrence	Interrupt venetoclax Once the toxicity has resolved to Grade 1 or baseline level, venetoclax therapy may be resumed at the same dose. No dose modification is required.	
	2 nd and subsequent occurrences	Interrupt venetoclax. Follow dose reduction guidelines in Table 5 when resuming treatment with venetoclax after resolution. A larger dose reduction may occur at the discretion of the investigator.	
	Hem	natologic Toxicities	
Grade 3 or 4 neutropenia with infection or fever; or Grade 4 hematologic toxicities (except lymphopenia)	1 st occurrence	Interrupt venetoclax. To reduce the infection risks associated with neutropenia, granulocyte-colony stimulating factor (G-CSF) may be administered with venetoclax if clinically indicated. Once the toxicity has resolved to Grade 1 or baseline level, venetoclax therapy may be resumed at the same dose.	
	2 nd and subsequent occurrence	Interrupt venetoclax. Consider using G-CSF as clinically indicated. Follow dose reduction guidelines in Table 5 when resuming treatment with venetoclax after resolution. Additional dose reductions may occur at the discretion of the physician.	

Consider discontinuing venetoclax for subjects who require dose reductions to less than 100 mg for more than 2 weeks.

Management of Neutropenia

Based on clinical observations with the 1st generation Bcl-2 inhibitor, navitoclax and in vitro colony-forming assays to assess Bcl-2-selective inhibitor effects on granulocyte precursors, it is possible that subjects treated with venetoclax might experience neutropenia. Subjects with a history of neutropenia, who have received multiple prior therapies and/or have significant bone marrow involvement, may be at particular high risk. If determined to be clinically indicated by the treating physician in compliance with ASCO guidelines, G-CSF may be administered during dosing of venetoclax. The use of G-CSF support is strongly recommended for subjects with Grade 4 neutropenia (ANC < $500/\mu$ L). If the subject presents with febrile neutropenia or Grade 4 neutropenia for more than one week despite the use of optimal G-CSF support, venetoclax dosing should be interrupted until ANC recovery to > $500/\mu$ L. Venetoclax may then be re-initiated at a

Adverse reactions were graded using NCI CTCAE version 4.03.

b. Clinical TLS was defined as laboratory TLS with clinical consequences such as acute renal failure, cardiac arrhythmias, or sudden death and/or seizures.

lower dose as defined in the following table. Subjects not responding to G-CSF despite venetoclax interruption should undergo further evaluation to determine the etiology of the neutropenia.

Table 5. Dose Modification for Toxicity during Venetoclax Treatment.

Venetoclax Dose	Reduced Dose	
400 mg	300 mg	
300 mg	200 mg	
200 mg	100 mg	
100 mg	50 mg	
50 mg	Re-challenge at 20 mg ^a	

a. Subjects who do not tolerate 20 mg will discontinue venetoclax, but may remain on study to assess for progression.

Management of Lymphopenia

There is a potential for clinically significant lymphopenia in this study. If clinically indicated, anti-infective prophylaxis should be implemented at the investigator's discretion, including appropriate prophylaxis for viral, fungal, bacterial or Pneumocystis infections. Potential for drug-drug interactions should be considered. Most anti-fungals are excluded and other commonly used agents may be cautionary or prohibited due to drug-drug interactions.

Management of Hematologic Toxicities Other Than Neutropenia or Lymphopenia

Venetoclax treatment should be withheld for any Grade 4 hematologic toxicity. Once the toxicity has resolved to Grade 1 or baseline level (recovery), venetoclax may be re-started at the same dose. If the toxicity recurs, the dose reduction guidelines in Table 4 should be followed when resuming study treatment following resolution. Additional dose reductions may occur at the discretion of the physician.

Management of Non-Hematologic Toxicity

Venetoclax treatment should be withheld for any clinically relevant Grade ≥3 non-hematologic toxicity. Once the toxicity has resolved to Grade 1 or baseline level (recovery), venetoclax may be re-started at the same dose. If the toxicity recurs, the dose reduction guidelines in Table 4 should be followed when resuming study treatment following resolution. Additional dose reductions may occur at the discretion of the physician.

Management of Decrease in Spermatogenesis

Based on findings in a preclinical study, there is a potential for decreased spermatogenesis. Male subjects should consider sperm banking before treatment with venetoclax if they are considering preservation of fertility.

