6.0 Treatment Plan / Study Procedures

Table 3. Schedule of Events

		Cycle 0								
	Screen (within 30	_,								
Day(a)	day unless noted)	Day 1	day 2	day 3	day 4	day 22				
MD Visit	x	x	uu, z	udy 5	uuy 4	uuy 22				
Vitals signs	×	x	x	x	×	×				
vitais signs	•		_	 						
CBC diff	×	x	x	x	x	x				
CMP (b)	×	x	x	x	x	x				
Phos	_ ^	×	×	×	×	×				
Uric acid		х	x	x	х	×				
LDH		×	х	х	х	×				
Correlative Lab Draw		x		_ ^_	•					
CONTENTIVE LOS DIAW										
Hep B serologies	×									
The production of the producti										
Methylprednisolone		1000 mg/m2	1000 mg/m2	1000 mg/m2						
Rituximab		100 mg	375 mg/m2		375 mg/m 2					
Ritaxiiiiab		100 mg	373 mg/mz	373 mg/mz	373 mg/m2					
Ct or MRI thorax (c)	x					x{d}				
CT or MRI abdomen/pelvis (c)	×					x{d}				
Ci di wiki abdomeny pervis (c)	- ^					×(u)				
				 						
				1					 	
NOTES										
NOTES	() 5			0.1	a. L. (anh. 1.	avala narmitta	d if aubicat appallac	l ofter pretend	LuE approval)	
	(a) Protocol allowed									
	(b) CMP includes th bilirubin, alkaline pl		a, K, Chloride, I	oicarbonate, B	UN, creatinine,	giucose; calci	um; total protein, al	pum in, AST, A	LI, total	
	(c) MRI is allowed		lle control adio	atad						
	(d) Areas that did				1 F am in I	auta da ast o				
	(a) Areas that did i	iot nave enlarg	ea lymph noae	es greater than	1.5 cm in long	-axis do not re	equire re-im aging			
										I

	Cycle 1 (35 days)									
Day (a)	1	2	8	9	15	16 (d)	22	23 (d)	29	30 (d)
MD Visit	×		6	9	13	10 (u)	22	23 (u)	29	30 (u)
Vital signs	×									
vital signs										
CBC diff	×	×	×	×	×	x	×	x	×	x
CMP (b, c)	x (pre and 6-8 hr)	x{c}	x (pre and 6-8 hr)	x (c)	×	x	×	×	x	x
Phos (b)	x (pre and 6-8 hr)	x {c }	x (pre and 6-8 hr)	x {c }	x	x	×	x	x	x
Uric acid (b)	x (pre and 6-8 hr)	x (c)	x (pre and 6-8 hr)	x (c)	x	x (c)	x	x (c)	x	x{c)
LDH (b)	x (pre and 6-8 hr)	x {c }	x (pre and 6-8 hr)	x {c }	x	x (c)	x	x {c }	x	x{c)
Correlative Lab Draw	x									
Investigat Administration for TLC or extension in indicated (d)										
Inpatient Admission for TLS monitoring in indicated (d)	×	X	×	X						
				50 may	100 mg		200 mg		400 mg	
		20 mg x 6		50 mg x 6 day	x 7 day		x 7 day		x1wk	
Venetoclax (IDS) (e)	20 mg x 1	day supply		supply	supply		supply		supply	
		,								

NOTES

- (a) Protocol allowed date windows for Cycle 1 are 0 days or + 14 days. In other words, patients should take 7 days of each venetoclax dose level prior to dose escalation.

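### Section 7.3.4 gives two conflicting default venetoclax rules for a first afebrile Grade 4 neutropenia and does not say which governs

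*Combined protocol and SAP*

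**What the plan says.** Both rules are in Section 7.3.4 (Dose Adjustment and Management of Toxicity).

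**Table 4.** Its title is "Table 4. Venetoclax Recommended Dose Modification for Toxicities". The haematologic row covers "Grade 3 or 4 neutropenia with infection or fever; or Grade 4 hematologic toxicities (except lymphopenia"). At a first occurrence the action is to interrupt, with G-CSF optional, and then: "Once the toxicity has resolved to Grade 1 or baseline level, venetoclax therapy may be resumed at the same dose". Reduction to a Table 5 dose starts at the second occurrence.

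**Management of Neutropenia paragraph.** G-CSF may be given while venetoclax continues, and is strongly recommended at Grade 4 (ANC below 500/µL). Interruption is called for "If the subject presents with febrile neutropenia or Grade 4 neutropenia for more than one week despite the use of optimal G-CSF support". In that case "venetoclax dosing should be interrupted until ANC recovery to" above 500/µL, after which venetoclax may restart at a "lower dose as defined in the following table". That table is Table 5, which steps 400 mg down to 300 mg and 200 mg down to 100 mg. The paragraph makes no exception for a first event.

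**Pointer.** The lead-in to the section reads "See Table 3 for dose modifications for hematologic and other toxicities related to venetoclax", but in this protocol that number belongs to "Table 3. Schedule of Events" in Section 6.0.

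**The concern.** A patient on venetoclax whose ANC falls below 500/µL for the first time, without fever or infection, falls under both texts. Table 4 stops the drug that day. The paragraph keeps it going with G-CSF for a week or more, and calls for no interruption if the count recovers within the week. Two patients with the same event could therefore be managed differently, each in line with a stated rule.

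Patient safety is at stake first, since one rule continues dosing at an ANC where the other withholds the drug. The descriptive summaries of dose modifications, interruptions and their reasons (Sections 9.6 and 9.8) would also mix two policies, so a count of interruptions would partly reflect which text the investigator followed.

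**Working it through.** The plan gives no figure to reproduce. The check sets the two rules side by side for a first event.

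| Point | Table 4 | Management of Neutropenia |
|---|---|---|
| Afebrile Grade 4: when to interrupt | At onset | After more than one week of Grade 4 on optimal G-CSF |
| Febrile neutropenia: when to interrupt | At onset | At presentation (natural reading) |
| ANC for restart | Grade 1 or baseline | Above 500/µL |
| Restart dose | Same dose | One Table 5 step lower |

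A first afebrile Grade 4 event differs on trigger, restart ANC and restart dose. A first febrile event differs on restart ANC and dose only. From the second occurrence both texts reduce the dose; the afebrile trigger still differs, and Table 4 then asks only for resolution.

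**Restart dose (Table 5).**
- At 400 mg: (400 − 300)/400 = 25% lower under the paragraph.
- At 200 mg: (200 − 100)/200 = 50% lower.

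**Restart ANC.** On the iwCLL scale in Section 10.0, Grade 1 starts at 1,500/µL. For baseline ANC B, the gap between the two restart thresholds is min(1,500, B) − 500:
- B of 1,500 or more: 1,000/µL.
- B = 1,000: 500/µL.
- B = 500: zero.

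Low baselines are possible, because inclusion criterion 9 waives its ANC limit of 500/µL when the cause is marrow infiltration. Two facts limit this calculation. A note beside Table 4 cites CTCAE 4.03, whose neutrophil cut-offs the documents do not reproduce. And Section 10.0 makes a patient with pre-therapy ANC below 1,000/µL not evaluable for ANC toxicity on the iwCLL scale, so on that scale Table 4's grade-based trigger is undefined for such a patient.

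**Trigger, illustration only.** Assume 400 mg daily, detection at onset and one full week of Grade 4: 7 × 400 = 2,800 mg given under the paragraph and withheld under Table 4. Scheduled blood counts come once per 28-day cycle in Cycles 2–6 and every third cycle from Cycle 7, so detection at onset is not assured.

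**Precedence.** Two readings might reconcile the texts.
- *Sequential:* Table 4 for short episodes, the paragraph for long ones. This fails, because the paragraph's interruption after a week presumes that dosing continued, while Table 4 has already stopped it.
- *Specific over general:* a later subsection restates the Table 4 rule for haematologic toxicities other than neutropenia and lymphopenia, which suggests that neutropenia follows its own paragraph. Against that, the Table 4 row names neutropenia, mentions G-CSF and excepts only lymphopenia.

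The general advice in Section 2.2.3.2, to interrupt or reduce for severe neutropenia, does not choose between them.

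**The case against.** The strongest reply is structural. Section 7.3.4 has a separate subsection for each kind of toxicity, and the one that repeats the Table 4 rule leaves neutropenia out. If Table 4 governed neutropenia, that exclusion would serve little purpose. This is a fair inference and leans toward the paragraph. It does not settle the matter, because the Table 4 row includes neutropenia by name.

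A reader might go further and infer that no investigator can comply with both texts. The documents do not support that. Table 4 is only recommended, both restart sentences are permissive, and one conservative course satisfies both: stop at onset, wait for Grade 1 or baseline, resume lower. But nothing directs the investigator to that course, and following the paragraph's default departs from Table 4's plain instruction to interrupt.

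A reader might also infer that Table 4 was the intended rule or is shown to be safer. The documents show neither. The paragraph pairs continued dosing with strongly recommended G-CSF, and Section 6.8 lets the investigator stop therapy on safety grounds. Calling Table 4 the more cautious trigger is a judgement for the medical lead to confirm.

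It also stands that the safety analysis of 17 patients is descriptive, that Section 9.6 collects interruptions and their reasons (so differing management would be visible), and that the wrong table number is clerical.

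**Conclusion.** The conflict is real and should be corrected. For a first afebrile Grade 4 neutropenia the default rules differ on trigger, restart ANC and restart dose; for a first febrile neutropenia, on restart ANC and dose. The febrile comparison assumes that the one-week condition qualifies only Grade 4 neutropenia. The restart-dose gap is 25% at 400 mg and 50% at 200 mg. The restart-ANC gap is at most 1,000/µL on the iwCLL scale and shrinks to nothing as baseline ANC falls to 500/µL. The 2,800 mg figure is an illustration, not an expected exposure difference.

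The number of patients affected is unknown. Section 2.2.3.2 gives Grade 3 or 4 neutropenia in 41% (98/240) on venetoclax and Grade 3 or above in 53.1% of 49 on venetoclax plus rituximab, but no rate of afebrile Grade 4.

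A reader might suspect that the main result is at risk. It is not: debulking is assessed in Cycle 0, before venetoclax starts. The effect is confined to patient safety and to the descriptive dose-modification and interruption data.

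**What to change.** Keep one rule for neutropenia and have the other text refer to it.

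- **Rule.** The more cautious trigger is Table 4: interrupt at Grade 4 onset, or at Grade 3 or 4 with fever or infection. The sponsor's medical lead should confirm the rule, one numeric recovery ANC and one restart dose after a first event.
- **Scale.** State which scale defines the grades in Table 4, since the adjacent note cites CTCAE 4.03 and Section 10.0 uses iwCLL.
- **Trigger as a number.** Express it as an ANC value, so that it also covers patients with pre-therapy ANC below 1,000/µL, and say what applies to a patient who enters already below that value.
- **Clerical.** Change the lead-in pointer from Table 3 to Table 4.

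The amendment itself is wording only, but the choice has a clinical cost. If Table 4 governs, interruptions will be more frequent and longer. Some may pass the Section 7.3.4 limits (more than 1 week in ramp-up, more than 2 weeks at 400 mg) that call for TLS reassessment and possibly repeating part or all of the ramp-up. In a trial about TLS risk, the medical lead should weigh that when setting the recovery ANC.

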8.0 Evaluation of Response

8.1 Assessment of Tumor Burden

Earlier clinical trials with venetoclax identified risk factors for tumor lysis syndrome, in particular measurements of tumor burden, including maximum lymph node diameter and absolute lymphocyte count. Subjects have been classified in 3 risk categories based on risk for developing medically concerning TLS with venetoclax administration. The tumor burden assessed by the nodal disease and absolute lymphocyte count has been used to define each category as below:

Tumor Burden Category	Criteria
Low	All measurable lymph nodes with the largest
	diameter < 5 cm by radiologic assessment
	AND ALC < 25k/uL
Medium	Any measurable lymph node with the largest
	diameter >/= 5 cm but < 10 cm by radiographic
	assessment OR ALC >/= 25k/uL
High	Any measurable lymph node with the largest
	diameter >/= 10 cm by radiologic assessment
	OR
	ALC >/= 25k/uL AND any measurable lymph
	node with the largest diameter >/= 5 cm

8.2 International Working Group CLL (iwCLL) Clinical Response Assessment

Criteria for response will utilize the 2008 IWCLL Guidelines for response, which includes clinical, hematological, and bone marrow feature:

Complete response: Requires all of the following for a period of at least two months from completion of therapy:

- Absence of significant lymphadenopathy (e.g. >1.5cm in diameter) on physical exam;
- No hepatomegaly or splenomegaly on physical exam;
- Absence of constitutional symptoms;
- Blood counts within the following values: lymphocytes < 4,000/uL, polymorphonuclear leukocytes >1500/ μ L, platelets >100,000/ μ L, hemoglobin >11.0 g/dL (untransfused); absences of clonal lymphocytes;
- Bone marrow aspirate and biopsy must be normocellular for age with <30% of nucleated cells being lymphocytes. Lymphoid nodules must be absent. If the marrow is hypocellular, a repeat determination should be performed in one month.
- The marrow should be analyzed by flow cytometry and/or immunohistochemistry to demonstrate that the marrow is free of clonal B- CLL cells.
- A CT scan or MRI documenting absence of significant lymphadenopathy should be performed if previously abnormal.

• Patients who fulfill the criteria for CR after induction with the exception of a persistent cytopenia that is believed to be treatment related will be considered CR with incomplete bone marrow recovery (CRi). Additionally, patients who fulfill the criteria of CR with exception of having bone marrow lymphoid nodules will be considered a nodular PR.

Partial response: Requires at least 2 of the following criteria from group A, and at least one of the criteria from group B, and for a period of at least 2 months:

Group A:

- ≥50% decrease in peripheral absolute lymphocyte count from pretreatment value, or less than 4,000/uL
- ≥50% reduction in lymphadenopathy by examination or scan, or less than 1.5cm in size.
- ≥50% reduction in splenomegaly (cm below costal margin) by examination or scan
- ≥50% reduction hepatomegaly (total liver span) by examination or scan
- 50% reduction in marrow infiltrate or B-lymphoid nodules

Group B:

- Polymorphonuclear leukocytes ≥1,500/µL or 50% improvement from pre-treatment value:
- Platelets >100,000/µL or 50% improvement from pre-treatment value;
- Hemoglobin >11.0 g/dl (un-transfused) or 50% improvement from pre-treatment value.

Progressive Disease: Characterized by any one of the following events:

- ≥50% increase in the products of at least two lymph nodes on two consecutive determinations two weeks apart (at least one lymph node must be ≥2 cm); appearance of new palpable lymph nodes.
- ≥50% increase in the size of the liver and/or spleen as determined by measurement below the respective costal margin; appearance of palpable hepatomegaly or splenomegaly, which was not previously present.
- An increase in the number of blood lymphocytes by 50% or more with at least 5000 B lymphocytes per microliter.
- Transformation to a more aggressive histology (i.e., Richter's syndrome or prolymphocytic leukemia with ≥56% prolymphocytes).
- During therapy, patients not fulfilling the above criteria for progressive disease but demonstrating a decrease in hemoglobin >2 gm/dL, decrease >50% in platelet or granulocyte

count will not be rated as progressive disease because these may occur as both a consequence of therapy. A bone marrow biopsy in such settings is strongly encouraged.

After treatment, The progression of any cytopenia (unrelated to autoimmune cytopenia), as documented by a decrease of Hb levels by more than 20 g/L (2 g/dL) or to less than 100 g/L (10 g/dL), or by a decrease of platelet counts by more than 50% or to less than 100×109 /L ($100\,000/\mu$ L), which occurs at least 3 months after treatment, defines disease progression, if the marrow biopsy demonstrates an infiltrate of clonal CLL cells.

Stable Disease: Patients who do not fulfill the criteria for complete or partial response as defined above but do not exhibit progressive disease will be considered as having stable disease.

